Randomization will be done by the Clinical Center pharmacy Protocol Support Service and will be stratified by the result of the liver biopsy (classified as definite steatohepatitis, steatosis without steatohepatitis, or borderline^{21, 22}) and by the presence or absence of diabetes mellitus type 2 at enrollment. Patients will be monitored on weeks 1, 2, 3, 4, 8, 12, 16, and 20 of treatment. On each visit, fasting blood tests for Chem-20, insulin, C-peptide, free fatty acids and vitamin E levels will be drawn, vital signs including weight will be measured and a symptom questionnaire will be administered. CBC, lipid panel, apolipoproteins and urinalysis will be drawn every 4 weeks. A nurse will determine weight, vital signs and symptoms on every visit. A physician will evaluate the patients every 4 weeks. A serum sample for research purposes will be drawn on each visit and stored in -80°C.

On week 4 of treatment, patients will be admitted for a second liver biopsy and adipose tissue biopsy, and will have a repeat of the MR spectroscopy and FSIVGTT.

On week 24 of treatment, all patients will be admitted for an exit work-up, identical to the detailed in-patient assessment described above, but without the biopsies.

During the treatment, patients will be recording medication intake on a diary that will be collected every visit and will be used to assess compliance.

Extended Treatment Phase

On discharge, all patients will be offered to continue treatment with open-label vitamin E 800 IU/d (two 400 IU capsules taken once daily) for up to 120 more weeks, after which, an exit liver biopsy will be performed. Enrollment into the extended treatment phase is optional and refusal will not exclude the patient from the study. The medication intake diary will be used in this phase as well.

After 24 weeks in the extended phase (week 48 of the study), patients will undergo an additional MR spectroscopy. Based on the results of the MRS and liver enzymes, the response will be assessed prior to deciding on treatment continuation. For this purpose, response is defined as a decline of >=25% in ALT or normal ALT or normal AST or an absolute decline of more than 2% in liver fat content by MRS. The response criteria are selected to be sensitive, but not necessarily specific, aiming to predominantly identify patients who are not responding to treatment and in which continuation is futile. Based on the response assessment there are three possible outcomes (Figure 4):

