⁵ NK/NKT cell analyses – On Run-in phase, first admission and week 144 will be drawn for all patients. On weeks 4 and 24 these will be performed only on the 200 IU/d and 800 IU/d arms (total volume 48 ml). On week 144 only 30 ml will be obtained. Will not be performed if Hb < 10 g/dL.

⁶ FSIVGTT – total blood volume drawn 120-150 ml. Will not be performed if Hb < 10 g/dL.

⁷ Possible lowering of vitamin E dose based on week 48 results (see Figure 4).

Analysis of the study

End points

Primary end points

There are two primary clinical end points in the study. The primary biochemical response is defined in a binary manner as an end-of-treatment AST <=32 or ALT <=35 U/L. The selection of these cut-off values is based on a pilot analysis by us that examined in an unbiased manner several rules for biochemical response and found this to be the one most strongly associated with histological response to treatment, irrespective of treatment modality³¹. We will also analyze the absolute change in ALT and AST from pre-treatment to end-of treatment as continuous parameters of the effect of treatment on liver enzymes. Patients who at the time of starting vitamin E treatment have normal liver enzymes will be excluded from this analysis. The primary physiological response is the absolute change in liver fat content as determined by comparing the ¹H-MRS results from pre-treatment to end of treatment.

Secondary end points

Secondary end points include: absolute and percent decrease in liver enzymes, decrease in GGT levels, percent reduction in liver fat.

A secondary analysis will analyze the effect of the lifestyle modification by comparing the end points between enrollment and the end of the lifestyle modification phase. Another analysis will determine the effect of increasing the dose of vitamin E by comparing the end points between the end of the randomized phase (week 24) to weeks 24 and 144 of the extended phase.

The kinetics of response will be determined by analyzing sequential ALT and AST measurements. Current data suggest biphasic response pattern to vitamin E and mathematical modeling will be applied to the results and will be compared between doses. Similar modeling will be applied to changes in liver fat content by ¹H-MRS.

Basic scientific end points

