Gene expression in liver and adipose tissue will be analyzed using microarray and quantitative PCR (qPCR) of tissue samples. Treatment-induced changes or comparisons between groups of patient (i.e. comparison of baseline expression between responders and non-responders) will be expressed as fold-induction.

NK and NKT cell changes in the serum and liver tissue will be analyzed using phenotyping and functional assays.

Oxidative stress will be measured in the serum, urine, liver and adipose tissue using TBARS assay, F₂-isoprostanes, 9-HODE, 13-HODE, SOD activity or similar measures. In women of child-bearing age, the phase of the menstrual cycle will be recorded on extended visits, as F₂-isoprostane levels can be affected by it.

Statistical analyses

Parameters of response to treatment will be analyzed by matched-pair comparison between pre-treatment and end of treatment values. Student's t-test will be used for values that are distributed normally while Wilcoxon's sign-ranked test will be used for non-parametric values. Categorical comparisons will be performed using X^2 or Fisher's exact test, as appropriate. The Cochran-Armitage test for trend will be used to test for a dose effect on the primary clinical end points.

To determine the effect of genetic variants, genotype-based analyses will be preferred to allelic analyses, with an additive model used primarily, unless other (dominant or recessive) models seem more appropriate. Linear or ordinal logistic regression will be used.

All analyses will be done with and without stratification for the presence of diabetes mellitus.

An $\alpha \le 0.05$ will be used to determine statistical significance.

Sample size calculation

The main goal of the study is to understand and characterize the mechanism of response to vitamin E. An important goal of the study is to simultaneously collect liver and adipose tissue to determine the site of action of the vitamin E and the relative contribution of each tissue to the disease. For most of the planned end points, including changes in liver fat content by ¹H-MRS and the basic scientific end points, there is not enough pre-existing data to allow for accurate sample size calculation.

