For the comparison of effectiveness between different doses of vitamin E (primary aim 1), the primary biochemical end point will be used. We assume a response rate of 45% with the 800 IU/d dose (similar to that seen at the PIVENS trial), a 10% response rate to the 200 mg/d dose and a 20% response to the 400 mg/d dose. Under these assumptions, a sample size of 25 patients per group will give a power of 80% to detect a linear trend with statistical significance of 5% (Cochran-Armitage test). To account for possible drop-out and loss to follow-up, we are aiming to recruit 30 patients per group or an overall of 90 patients in the study.

As the sample size calculation is limited by the absence of published data, we will re-assess our calculations after 10 patients have been enrolled in each arm, and again after 20 have been enrolled

Human subject protections

Rationale for subject selection

The study is designed to enroll patients with NAFLD that can be potentially benefit from treatment. Currently, there are no reliable non-invasive markers that accurately distinguish NASH from steatosis only, although the latter seems to carry a more favorable prognosis. For patients with steatosis only, it is unclear whether treatment can improve their disease and prevent progression to NASH. In most clinical trials with histological end points, patients with steatosis only were excluded as they cannot show significant histological

improvement. In this study, with a primarily scientific outcome, we are interested in studying the effect of vitamin E on these patients as well and we consider the intervention to be low-risk enough to allow us to recruit all patients with NAFLD.

The exclusion criteria for the study are mainly geared towards limiting enrollment to patients for whom treatment is considered safe and that have no confounders that would limit the analysis of the results. There are no limitations based on race or ethnicity. However, we anticipate that very few patients of African ancestry will be enrolled, because of the scarcity of NAFLD in these patients and their apparent "protection" from liver fat accumulation.

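### The Cochran-Armitage test assigned to both primary clinical end points cannot be run on the continuous liver-fat change, and no other between-dose test is named for it or for the continuous ALT and AST changes

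*Combined protocol and SAP*

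**What the plan says.** Under Primary end points: "There are two primary clinical end points in the study". The first is a yes/no biochemical response, based on AST and ALT cut-offs at end of treatment. The second is a measurement: "The primary physiological response is the absolute change in liver fat content", from pre-treatment to end of treatment by MRS. The same paragraph also plans absolute change in ALT and AST as continuous measures of the treatment effect on liver enzymes.

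Under Statistical analyses, the dose effect is given one method: "The Cochran-Armitage test for trend will be used to test for a dose effect on the primary clinical end points". The other methods named there are:

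- Student's t and Wilcoxon signed-rank tests, which follow the sentence "Parameters of response to treatment will be analyzed by matched-pair comparison between pre-treatment and end of treatment values".
- Chi-square or Fisher's exact tests, for categorical comparisons.
- Linear or ordinal logistic regression, in the paragraph on genetic variants.

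Under Secondary end points, for the ALT and AST time course, "mathematical modeling will be applied to the results and will be compared between doses". Similar modelling is promised for liver fat. Neither a model nor a test is specified.

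Under Sample size calculation: "For the comparison of effectiveness between different doses of vitamin E (primary aim 1), the primary biochemical end point will be used".

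**The concern.** The plural in the Cochran-Armitage sentence matches the two end points listed under Primary end points, so the plan promises this test for both. The test compares proportions across ordered groups. A change in fat fraction is not a proportion of responders, and no rule turns it into one for the primary analysis.

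The between-dose comparison carries most of the inferential weight here. There is no placebo arm (Absence of a control arm). The Run-in phase and lifestyle intervention section accepts that lifestyle change may contribute to the observed effect in all arms alike, and says that the contribution of vitamin E will be inferred from how response varies with dose. The Précis likewise says that the phenotyping before and after treatment, which includes radiological testing, serves to characterise dose response. A paired test of liver fat before and after treatment cannot show a dose response. If the between-dose method, dose scores and covariates stay open for a primary end point, they can be chosen after the results are known.

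**Working it through.** **1. Which named method can test a dose effect on which outcome**

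| Method in the plan | Compares doses? | Runs on a continuous change? |
|---|---|---|
| Cochran-Armitage | yes | no, needs a binary outcome |
| t or signed-rank, matched pairs | no, pre versus post | yes |
| Chi-square or Fisher | could, for categories | no |
| Linear or ordinal regression | named only for genotype | linear could, but is not assigned to dose |
| Kinetic modelling (secondary) | yes, in words | no model or test given |

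No row gives a between-dose test assigned to liver-fat change, or to ALT or AST change. The one liver-fat threshold in the documents, "an absolute decline of more than 2% in liver fat content by MRS", sits under Extended Treatment Phase. There it is one of several alternative criteria for the week-48 decision on continuing treatment. It does not define a liver-fat responder at week 24.

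**2. The plan's own power figure reproduces for the binary end point**

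Inputs (Sample size calculation): response rates 10%, 20% and 45%; n = 25 per group; 5% significance, taken as two-sided.

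Formula: with scores centred as d, power = Φ[(Σnpd − 1.96·s0)/s1], where s0² = p̄(1−p̄)Σnd² and s1² = Σnp(1−p)d².

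With scores 1/2/3, d = −1, 0, 1 and p̄ = 0.25:

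- Σnpd = 25 × (0.45 − 0.10) = 8.75
- s0 = √(0.25 × 0.75 × 50) = 3.062
- s1 = √[25 × (0.09 + 0.2475)] = 2.905
- power = Φ[(8.75 − 6.001)/2.905] = Φ(0.946) = 82.8%

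A continuity correction of 0.5 gives 78.1%, and the exact conditional test gives 79.7%. Scores 200/400/800 give 83.8%, 81.0% and 81.2% in the same order. The stated 80% is therefore sound. The drop-out step also holds: 25/(1 − 1/6) = 30 per group, 90 in total. Only response proportions enter this calculation, so it has no counterpart for liver-fat change.

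**3. What a runnable liver-fat trend test could detect (orientation only)**

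Assumptions, none of them in the documents: normal data, an effect linear in dose, a two-sided 5% t-test of the slope. The documents give no SD, so results are in SDs of the change.

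- Mean score (200 + 400 + 800)/3 = 466.67
- Sum of squared deviations 71,111 + 4,444 + 111,111 = 186,667 (from unrounded values)
- SE of the 800 versus 200 difference at 25 per arm = 600/√(25 × 186,667) = 0.278 SD
- 80% power (noncentral t, 73 df) at 0.789 SD; 0.803 SD with equally spaced scores
- At 20 per arm 0.885 SD; at 30 per arm 0.718 SD

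**4. Effect of adjusting for pre-treatment fat**

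The adjusted model was simulated at a difference of 0.789 SD, with biopsy class and diabetes assumed non-prognostic. For assumed pre/post correlations of 0.5 to 0.8 and post/pre SD ratios of 0.8 to 1.2, power runs from about 78% to 95%, against 80% for raw change. It is about level with raw change at ratio 1.2 and correlation 0.65 (80.2%), and lower at ratio 1.2 and correlation 0.8 (77.7%). Adjustment usually helps, but not always.

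**The case against.** The best defence is that the comparison of doses for primary aim 1 is assigned to the biochemical end point alone, that its power calculation reproduces, and that the plan says there were too few data to size the liver-fat end point. On that view the plural is a slip. This stands as far as it goes: nothing sized is lost, and no wrong number would appear, because the test simply cannot be run. It does not remove the contradiction. Either a liver-fat dose test is intended and unspecified, or none is intended and the sentence is wrong.

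A generous reader might take Cochran-Armitage loosely, as any linear trend test, or read Student's t-test as a comparison between doses. Neither reading settles a method. The first leaves scores and covariates open. The second sits badly with a sentence about matched pairs, and would leave the choice of dose pairs unstated.

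The section on the absence of a control arm argues that the lead-in should remove most of the placebo effect. Whether that makes pre/post changes interpretable is a separate question; even if it does, they do not compare doses.

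The choice of repair is also partly a matter of preference. A linear trend on the raw change would close the gap as well, and the power figures describe the repair rather than the defect.

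**Conclusion.** The point holds as a specification error that should be fixed. One of the two primary clinical end points is assigned a dose test that cannot be run on it, and no other between-dose test is named. The continuous ALT and AST changes under the same heading also lack one. This rests on the text alone and on no assumed value.

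Two stronger readings are not supported. A reader might infer that the trial has no valid dose test, or that its sample size fails; the Sample size calculation section ties both to the binary response, for which Cochran-Armitage is suitable and the 80% reproduces. A reader might also take 0.79 SD, or 78% to 95%, as the power of this trial for liver fat. Those figures depend on normal data and assumed correlations and SD ratios, and cannot be turned into fat-fraction points without an SD.

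**What to change.** 1. Limit the Cochran-Armitage sentence to the binary biochemical response.
2. Prespecify one linear dose-trend analysis for liver fat, with stated dose scores (for example 200/400/800). A suitable form models week-24 fat on dose, adjusted for pre-treatment fat and the randomization factors (biopsy class and diabetes). Report the slope and the per-dose means with 95% confidence intervals. Add a rank-based version as a fixed sensitivity analysis, not as a switch that depends on how the data look.
3. Use the same approach for the continuous ALT and AST changes.
4. If no dose test of liver fat is intended, correct the plural and say so.

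The general rule "All analyses will be done with and without stratification for the presence of diabetes mellitus" covers the whole plan and is left as it stands here.

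The cost is analysis wording only. Pre-treatment and week-24 MRS, biopsy class and diabetes status are already collected. The liver-fat model has 6 parameters (intercept, dose slope, pre-treatment fat, two for biopsy class, one for diabetes), leaving 75 − 6 = 69 residual degrees of freedom with 25 patients per arm.

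### The sized dose test takes no account of pre-treatment ALT and AST; adjusting for them needs no new data and may add about 1 to 10 points of power

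*Combined protocol and SAP*

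**What the plan says.** All references are to the combined protocol and SAP.

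- **Endpoint** (Primary end points): biochemical response is "defined in a binary manner as an end-of-treatment AST <=32 or ALT <=35 U/L". Either enzyme suffices.
- **Dose test** (Statistical analyses): "The Cochran-Armitage test for trend will be used to test for a dose effect on the primary clinical end points".
- **Sizing** (Sample size calculation): "We assume a response rate of 45% with the 800 IU/d dose (similar to that seen at the PIVENS trial"), with "a 10% response rate to the 200 mg/d dose and a 20% response to the 400 mg/d dose". From these, "a sample size of 25 patients per group will give a power of 80% to detect a linear trend" at the 5% level. The section gives the two lower doses in mg/d where the arms are in IU/d; the arithmetic does not depend on this.
- **Recruitment** (same section): "To account for possible drop-out and loss to follow-up, we are aiming to recruit 30 patients per group".
- **Use of baseline enzymes** (Primary end points): "Patients who at the time of starting vitamin E treatment have normal liver enzymes will be excluded from this analysis". Absolute ALT and AST change is also analysed; Statistical analyses describes pre-to-end-of-treatment comparisons as matched-pair tests.
- **Other factors**: randomization is stratified by biopsy class and type 2 diabetes (Vitamin E Treatment). Analyses are repeated with stratification for diabetes only (Statistical analyses).
- **Data available**: Chem-20 is drawn at the pre-treatment admission (Detailed in-patient assessment), and routine labs are taken again at week 0 of randomized treatment (Table 1).

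**The concern.** Because the limit is fixed, the fall a patient needs depends on where both enzymes start. On a log scale the distance to response is the smaller of ln(ALT/35) and ln(AST/32). It is above zero exactly when the patient does not already meet the rule. Two examples:

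- ALT 69, AST 47: ln(69/35) = 0.68 and ln(47/32) = 0.38. The distance is 0.38, a fall of 1 - 32/47 = 32% in AST.
- ALT 120, AST 36: ln(120/35) = 1.23 and ln(36/32) = 0.12. The distance is 0.12, a fall of 1 - 32/36 = 11% in AST, despite the much higher ALT.

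It is therefore plausible that this distance predicts response. A test that leaves out a prognostic baseline variable has less power than one that includes it. This dose comparison is the only one with a sample size calculation, and it carries the primary clinical aim. Neither the randomization strata nor the diabetes stratification brings enzyme level in.

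**Working it through.** **1. Reproduce the stated power.** Inputs from Sample size calculation: n = 25 per arm, rates 0.10, 0.20 and 0.45, alpha 5% (taken as two-sided; the section does not say). With scores -1, 0, 1:

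- Expected statistic: 25 × (0.45 - 0.10) = 8.75
- Null variance: 25 × 0.25 × 0.75 × 2 = 9.375 (SD 3.062)
- Variance under the alternative: 25 × (0.10 × 0.90 + 0.45 × 0.55) = 8.4375 (SD 2.905)
- Power: Φ[(8.75 - 1.96 × 3.062)/2.905] = Φ(0.946) = 82.8%

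Full enumeration of the three binomials gives 84.0%, or 79.7% with a continuity correction. With scores 200/400/800 the figures are 83.8% (approximation), 84.6% (enumeration) and 82.0% (corrected). The stated 80% stands. Expected responders: 25 × (0.10 + 0.20 + 0.45) = 18.75, about 19 of 75.

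**2. Gain by assumed prognostic strength.** The documents give no figure for this, so a range is used. Response follows a logistic model in a standardised baseline distance, with the arm rates held at 10/20/45% (10,000 trials per cell, equal scores, two-sided 5%).

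| Log-odds per SD (within-arm AUC) | Unadjusted, 25/arm | Adjusted score test, 25/arm | Adjusted, 20/arm (unadjusted 76%) |
|---|---|---|---|
| 0 (0.50) | 84% | 84% | 76% |
| 0.5 (0.64) | 84% | 86% | 77% |
| 1.0 (0.74) | 84% | 89% | 81% |
| 1.5 (0.82) | 84% | 92% | 86% |
| 2.0 (0.87) | 84% | 95% | 90% |
| 3.0 (0.93) | 84% | 98% | 95% |

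At log-odds 1.0, 1.5 and 2.0 the adjusted test at 25 per arm matches the unadjusted test at about 29, 32-33 and 37-38 per arm. With 25% response in every arm, the unadjusted test rejected in 4.8-5.1% of trials, the adjusted score test in 5.0-5.4% and the likelihood-ratio test in 5.4-6.1%.

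**3. Where the truth may lie in that range.** If ln(end value) = ln(baseline) + change, the log-odds per SD are about 1.8 × (baseline SD / change SD). Equal SDs give 1.8 (power about 94%). A ratio of one half gives 0.9 (about 88%). Regression to the mean lowers both.

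**4. Simulation on the enzyme scale.** Assumptions, none from the documents: ALT median 69 (IQR 54-89), AST median 47 (IQR 39-57), nobody meeting the rule at baseline, ALT-AST correlation 0.7, AST shift 0.7 times the ALT shift. There were 25 per arm, rates of 10/20/45% and 3,000 trials per cell (error about 0.7 points). Slope means the slope of the log end value on the log baseline value; below 1 it represents regression to the mean.

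| Slope | SD of log change 0.25 | 0.45 | 0.60 |
|---|---|---|---|
| 1.0 (unadjusted 83-84%) | adjusted 92% | adjusted 87% | adjusted 87% |
| 0.7 | gain 6 points | 2 | 1 |
| 0.5 | gain 4 points | 1 | 1 |

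At slope 0.3 the gain is 0 to 1.5 points, which is within or close to simulation error. A second simulation from the same medians and IQRs gave 83-85% unadjusted and 84-95% adjusted, a gain of about 1 to 10 points. Null rejection for the adjusted test was about 5-6%, and no setting lost power.

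**The case against.** The case for leaving the plan alone is substantial, and most of it stands as a limit on the size of this point.

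- **The planned test is valid and meets its target.** A reader might infer that the trial is underpowered, or that a chance imbalance in baseline enzymes biases the dose comparison. Neither is supported. The stated power reproduces, and under randomization the 5% error rate already allows for chance imbalance.
- **Prognostic strength is not documented.** A reader might infer that baseline level largely settles who responds. No section says so, and regression to the mean, to be expected after entry criteria that often require raised enzymes, could reduce the gain to a point or two. An example built on ALT alone would also overstate the matter, because a high ALT does not prevent response through AST.
- **Baseline is used elsewhere.** Absolute and percent enzyme changes and kinetic modelling by dose are planned. These are not the sized dose test. The planned re-assessments after 10 and 20 patients per arm concern sample size, not the choice of test.
- **Responders are few.** About 19 responders rule out a large model. They also argue against a trend test stratified by tertiles of distance: in one simulated setting the top tertile had 3% response, so 25 × 0.03 = 0.75, about one responder.
- **The covariate is new and the adjusted effect is conditional on baseline.** Both are true, and both can be handled by pre-specification and by showing raw rates.

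None of this is a reason against one pre-specified covariate. With a non-prognostic baseline, power was the same with and without adjustment, within simulation error.

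**Conclusion.** The point holds as an efficiency improvement. The sized test leaves out a plausible predictor that is already measured. Under the assumed enzyme distributions, adjustment adds about 1 to 10 points, from roughly 84% to 85-95% at 25 per arm. The upper end needs a small SD of change and little regression to the mean; the gain is zero if baseline is not prognostic. The size rests on the assumed medians, IQRs and change SDs, on the plan's own response rates, and on reading the exclusion of patients with normal enzymes as removing everyone who already meets the response rule.

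The gain would be worth more if evaluable numbers fall below 25 per arm. The allowance from 30 to 25 names only drop-out and loss to follow-up, not that exclusion. At 20 per arm the unadjusted test has about 76% power.

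**What to change.** In Statistical analyses, make the primary dose test for biochemical response the score test for dose trend in a logistic regression with one covariate: the smaller of ln(ALT/35) and ln(AST/32) before treatment. Name the visit that supplies the baseline value and the dose scores, which the plan does not give. Prefer the score test to the likelihood-ratio test, which ran slightly above 5%. Keep the unadjusted Cochran-Armitage test as a sensitivity analysis, and report raw response rates by arm beside the adjusted result.

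For the continuous enzyme analysis, regress ln(week-24 value) on dose and ln(baseline value), separately for ALT and AST, in place of a comparison of absolute change.

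The cost is a few sentences, settled before outcome data by arm are seen. No extra patients, visits or samples are needed. The price is a conditional effect estimate and a model that must stay at one covariate.
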